3.5 Toxicity Management Guidelines

All AEs should be assessed using NCI-CTCAE v5.0 criteria. **NOTE:** Hereafter in this Section, SL-279252 may be referred to as SL-279252 or as IP. Please see sections [5.5 Physician Availability Required for Administration of SL-279252](#) and [5.6 Monitoring Dose Administration](#). **NOTE:** Dose reductions of SL-279252 are not permitted except in the event of rechallenge after Grade 3 CRS as noted in the guideline below.

3.5.1 Management of Infusion-related Reactions

The data from the NHP studies indicate a potential risk for IRRs including CRS in humans dosed with SL-279252. The IRRs that were noted in cynomolgus monkeys were potentially cytokine-mediated as they a) demonstrated dose dependence and b) the severity of clinical symptoms correlated with cytokine level increases in the peripheral blood. It is important to note that the reactions that were noted in monkeys occurred during or immediately after SL-279252 infusion. Given the mechanism of action of SL-279252 (T cells become activated as they recognize tumor antigen), rapid onset of IRRs would be expected but the possibility of delayed reactions cannot be excluded. It is unlikely that SL-279252 infusion reactions are antibody-mediated type I or type 3, allergic HSRs as these reactions would not be expected to demonstrate dose dependence.

Differentiating between IRRs that are due to either the common non-allergic HSRs (e.g., CRS) or the rarer allergic HSRs can be challenging due to overlapping clinical manifestations. There are no specific clinical features (including symptoms and timing of reaction) that can absolutely distinguish between these two entities.

General guidance is provided below for IRRs secondary to both allergic and non-allergic HSRs e.g., CRS. These guidelines are not meant to be prescriptive. Established institutional guidelines should be followed where appropriate.

At the resolution of the event, the entirety of the data including clinical symptoms, response to treatment and laboratory studies should be re-evaluated to determine the final etiology of the event. For purposes of standardized reporting, utilize terms based on best medical judgement of the AE/SAE and the definition found in NCI-CTCAE v5.0 for IRR, allergic reaction, anaphylaxis, and CRS.

Primary prophylaxis against IRRs is not permitted to avoid obscuring a potential safety signal and to enable an assessment of whether pre-medications should be required for all subjects. However, as noted in the guidance below, secondary prophylaxis (i.e., prevention of IRRs following an initial episode) is appropriate and permitted at the discretion of the investigator.

NOTE: In the event of any Grade IRR (including CRS), subjects will be admitted for closer observation until resolution of symptoms.

Adverse Event	General Guidance for Infusion-related Reactions (IRRs) [Rosello, 2017; Porter, 2018]			
Infusion or Hypersensitivity Reactions		
Acute reactions to the IV administration of biologic agents is not uncommon. Reactions are either allergic reactions to foreign proteins or non-immune reactions. The term HSR is used to describe objectively reproducible signs or symptoms initiated by exposure to a defined stimulus at dose tolerated by a normal person. Allergy is HSR initiated by specific immunological mechanisms. Anaphylaxis is a severe, life threatening HSR. CRS consists of a non-allergic, cytokine mediated HSR. Differentiation between the common non-allergic HRS reactions and the rarer allergic HSR reactions can be challenging due to overlapping clinical manifestations. Fever, chills, rigors, headache, arthralgias, back pain, abdominal pain, nausea, vomiting, diarrhea, dyspnea, flushing, pruritus, and changes in heart rate and blood pressure are manifestations of common acute infusion reactions. Proinflammatory cytokines such as TNF-α and IL-6 may play a role in these reactions. Symptoms more suggestive of allergic HSR include generalized pruritus, urticaria, wheezing, frequent coughing, and anaphylactic symptoms. Subjects must be monitored for signs and symptoms of IRRs with prompt institution of treatment.
		
		
  
 Severity	Management	
  
	Severity	Management
Severity	Management			
		
  
 Grade 1	 
 Infusion interruption not indicated Admit to hospital for close observation until resolution of symptoms. Consider pre-medication (antipyretics, histamine (H)1 and H2 anti-histamines) for subsequent infusions per investigator/institutional guidelines 	
  
	Grade 1	
 Infusion interruption not indicated Admit to hospital for close observation until resolution of symptoms. Consider pre-medication (antipyretics, histamine (H)1 and H2 anti-histamines) for subsequent infusions per investigator/institutional guidelines
Grade 1	
 Infusion interruption not indicated Admit to hospital for close observation until resolution of symptoms. Consider pre-medication (antipyretics, histamine (H)1 and H2 anti-histamines) for subsequent infusions per investigator/institutional guidelines 			
		
  
 Grade 2	 
 Temporarily interrupt IP, or decrease the rate of the infusion by 50%, until resolution of the event. Begin IV infusion of normal saline and treat with antipyretics, histamine 1 and 2 (H1 and H2) anti-histamines. Corticosteroids and/or bronchodilator therapy may also be administered as appropriate. Monitor subject until resolution of symptoms. If the infusion is interrupted, then restart the infusion at no more than 50% of the rate at which the reaction symptoms occurred If no further symptoms are experienced, infusion rate may be escalated at intervals and increments as clinically appropriate If symptoms recur, then no further investigational product (IP) will be administered at this visit. Admit to hospital for close observation until resolution of symptoms. The following prophylactic pre-medications are recommended for future infusions: antipyretics, anti-histamines with/without corticosteroids per institutional guidelines 	
  
	Grade 2	
 Temporarily interrupt IP, or decrease the rate of the infusion by 50%, until resolution of the event. Begin IV infusion of normal saline and treat with antipyretics, histamine 1 and 2 (H1 and H2) anti-histamines. Corticosteroids and/or bronchodilator therapy may also be administered as appropriate. Monitor subject until resolution of symptoms. If the infusion is interrupted, then restart the infusion at no more than 50% of the rate at which the reaction symptoms occurred If no further symptoms are experienced, infusion rate may be escalated at intervals and increments as clinically appropriate If symptoms recur, then no further investigational product (IP) will be administered at this visit. Admit to hospital for close observation until resolution of symptoms. The following prophylactic pre-medications are recommended for future infusions: antipyretics, anti-histamines with/without corticosteroids per institutional guidelines
Grade 2	
 Temporarily interrupt IP, or decrease the rate of the infusion by 50%, until resolution of the event. Begin IV infusion of normal saline and treat with antipyretics, histamine 1 and 2 (H1 and H2) anti-histamines. Corticosteroids and/or bronchodilator therapy may also be administered as appropriate. Monitor subject until resolution of symptoms. If the infusion is interrupted, then restart the infusion at no more than 50% of the rate at which the reaction symptoms occurred If no further symptoms are experienced, infusion rate may be escalated at intervals and increments as clinically appropriate If symptoms recur, then no further investigational product (IP) will be administered at this visit. Admit to hospital for close observation until resolution of symptoms. The following prophylactic pre-medications are recommended for future infusions: antipyretics, anti-histamines with/without corticosteroids per institutional guidelines 			
		
  
 Grade 3	 
 Immediately discontinue infusion. Begin IV infusion of normal saline and treat with epinephrine, bronchodilators, diphenhydramine, ranitidine, corticosteroids, oxygen, fluids, vasoressors etc. as indicate and per institutional guidelines. Epinephrine is the drug of choice in an anaphylactic reaction and its administration should not be delayed. Admit to hospital for close observation until resolution of symptoms. Rechallenge should not be attempted in cases of true anaphylaxis. In other cases, once subject has completely recovered, carefully consider if it is safe for the subject to receive IP at the next scheduled dose with pre-medication (e.g., corticosteroids, anti-histamines, antipyretics) and slow infusion ($\leq 50\%$ of the rate at which the reaction occurred). If no further symptoms, rate may be escalated at intervals and increments as clinically appropriate. If symptoms recur, permanently discontinue IP 	
  
	Grade 3	
 Immediately discontinue infusion. Begin IV infusion of normal saline and treat with epinephrine, bronchodilators, diphenhydramine, ranitidine, corticosteroids, oxygen, fluids, vasoressors etc. as indicate and per institutional guidelines. Epinephrine is the drug of choice in an anaphylactic reaction and its administration should not be delayed. Admit to hospital for close observation until resolution of symptoms. Rechallenge should not be attempted in cases of true anaphylaxis. In other cases, once subject has completely recovered, carefully consider if it is safe for the subject to receive IP at the next scheduled dose with pre-medication (e.g., corticosteroids, anti-histamines, antipyretics) and slow infusion ($\leq 50\%$ of the rate at which the reaction occurred). If no further symptoms, rate may be escalated at intervals and increments as clinically appropriate. If symptoms recur, permanently discontinue IP
Grade 3	
 Immediately discontinue infusion. Begin IV infusion of normal saline and treat with epinephrine, bronchodilators, diphenhydramine, ranitidine, corticosteroids, oxygen, fluids, vasoressors etc. as indicate and per institutional guidelines. Epinephrine is the drug of choice in an anaphylactic reaction and its administration should not be delayed. Admit to hospital for close observation until resolution of symptoms. Rechallenge should not be attempted in cases of true anaphylaxis. In other cases, once subject has completely recovered, carefully consider if it is safe for the subject to receive IP at the next scheduled dose with pre-medication (e.g., corticosteroids, anti-histamines, antipyretics) and slow infusion ($\leq 50\%$ of the rate at which the reaction occurred). If no further symptoms, rate may be escalated at intervals and increments as clinically appropriate. If symptoms recur, permanently discontinue IP 			
		
  
 Grade 4	 
 Permanently discontinue IP Manage severe IRRs per institutional standards (e.g., epinephrine, diphenhydramine, ranitidine, corticosteroids, bronchodilators, oxygen, fluids etc.). Epinephrine is the drug of choice in an anaphylactic reaction and its administration should not be delayed Admit to hospital for close observation until resolution of symptoms. 	
  
	Grade 4	
 Permanently discontinue IP Manage severe IRRs per institutional standards (e.g., epinephrine, diphenhydramine, ranitidine, corticosteroids, bronchodilators, oxygen, fluids etc.). Epinephrine is the drug of choice in an anaphylactic reaction and its administration should not be delayed Admit to hospital for close observation until resolution of symptoms.
Grade 4	
 Permanently discontinue IP Manage severe IRRs per institutional standards (e.g., epinephrine, diphenhydramine, ranitidine, corticosteroids, bronchodilators, oxygen, fluids etc.). Epinephrine is the drug of choice in an anaphylactic reaction and its administration should not be delayed Admit to hospital for close observation until resolution of symptoms. 			

Adverse Event	General Guidance for Cytokine Release Syndrome (CRS) [Rosello, 2017; Porter, 2018]	
Cytokine-release	Severity (symptoms)	Management of CRS
	Grade 1	
 Decrease the rate of the infusion by 50%, until resolution of the event Maintain IV access. Symptomatic treatment with antipyretics, antiemetics, analgesics, H1/H2 antihistamines as needed; monitor fluid balance; assess for infection. Regularly evaluate for signs of further deterioration Admit to hospital for close observation until resolution of symptoms. For subsequent infusions, consider pre-medication (e.g., antipyretics, anti-histamines) per institutional guidelines
	Grade 2	
 Interrupt IP and do not-restart until symptoms are returned to grade ≤1 for at least 3 days. Once symptoms have resolved, administer dose per next scheduled time point. Start IV infusion with normal saline. Administer oxygen if needed. Treat with antipyretics, H1/H2 antagonists (diphenhydramine 50 mg IV plus ranitidine 50 mg IV), and/or methylprednisolone 1-2 mg/kg or equivalent dose of corticosteroid every 6 hours and manage per institutional guidelines. Closely monitor cardiac and other organ functions. Admit to hospital for close observation until resolution of symptoms. The next two subsequent infusions of SL-279252 (after an event of grade 2 CRS) must be administered in an inpatient setting for prolonged observation (e.g., 24 hours). For subsequent infusions, start infusion at 50% rate at which the symptoms occurred and titrate to tolerance. Consider pre-medication with dexamethasone 20 mg, antipyretics, H1/H2 anti-histamines, and manage per institutional guidelines. Subjects with extensive comorbidities or those of older age should be treated as for Grade 3. Subjects with worsening symptoms should be treated as for Grade 3
	Grade 3	
 Interrupt IP and do not-restart until symptoms are returned to grade ≤1 for at least 3 days. Once symptoms have resolved, administer dose per next scheduled timepoint. Admit to hospital for close observation until resolution of symptoms. For Grade 3 CRS, may consider rechallenge at the next lower dose level after consultation with medical monitor. After a Grade 3 CRS event, subjects must be premedicated with high dose steroids prior to the next infusion of SL-279252. If there is no evidence of CRS with the infusion at the reduced dose level, premedication with high dose steroids may be omitted for subsequent infusions. The two subsequent infusions of SL-279252 after an event of grade 3 CRS should be administered in an inpatient setting for prolonged observation (e.g., 24 hours). Any patient that experiences recurrence of Grade 3 CRS following re-treatment must be permanently discontinued from study treatment.

(Continued on next page)

Cytokine-release (continued from previous page)	Severity (symptoms)	Management of CRS
	Grade 3 (continued)	
 Monitor for organ dysfunction: admit to the intensive care or equivalent for close monitoring and management. Treat hypotension with IV fluid for blood pressure support and/or pressers. Administer oxygen for treatment of hypoxia. Cryoprecipitate or fresh frozen plasma may be required for coagulopathy. Manage per institutional guidelines. Administer tocilizumab at a dose of 8 mg/kg. If clinical improvement does not occur within 24 hours, administer a second dose of tocilizumab. Second-line therapies: 
 Methylprednisolone 2 mg/kg/day IV tapered over several days. For subjects with severe neurologic symptoms, consider using dexamethasone due to more efficient penetration of the blood-brain barrier. Anti-TNF-α mAbs (infliximab) or soluble TNF-α receptor (etanercept), or IL-1R-based inhibitors (anakinra).
	Grade 4	
 For Grade 4 CRS, permanently discontinue IP Admit to hospital for close observation until resolution of symptoms. Monitor for organ dysfunction: admit to the intensive care or equivalent for close monitoring and management Treat hypotension with IV fluid for blood pressure support and/or pressers. Administer oxygen for treatment of hypoxia. Cryoprecipitate or fresh frozen plasma may be required for coagulopathy. Manage per institutional guidelines. Administer tocilizumab at a dose of 8 mg/kg. If clinical improvement does not occur within 24 hours, administer a second dose of tocilizumab. Second-line therapies: 
 Methylprednisolone 2 mg/kg/day IV tapered over several days. For subjects with severe neurologic symptoms, consider using dexamethasone due to more efficient penetration of the blood-brain barrier. Anti-TNF-α mAbs (infliximab) or soluble TNF-α receptor (etanercept), or IL-1R-based inhibitors (anakinra).

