7.1 Assessment of Severity

The descriptions and grading scales found in the revised NCI-CTCAE version 5.0 will be utilized for AE reporting. A copy of these criteria can be downloaded from the website: https://ctep.cancer.gov/protocoldevelopment/electronic_applications/ctc.htm.

- **Grade 1:** Mild; asymptomatic or mild symptoms; clinical or diagnostic observations only; intervention not indicated
- **Grade 2:** Moderate; minimal, local or noninvasive intervention indicated; limiting age appropriate instrumental ADL*
- **Grade 3:** Severe or medically significant but not immediately life-threatening; hospitalization or prolongation of hospitalization indicated; disabling; limiting self-care ADL**
- **Grade 4:** Life-threatening consequences; urgent intervention indicated
- **Grade 5:** Death related to AE

*Instrumental ADL refer to preparing meals, shopping for groceries or clothes, using the telephone, managing money, etc.

** Self-care ADL refer to bathing, dressing and undressing, feeding self, using the toilet, taking medications, and not bedridden.

For AEs not included in the NCI-CTCAE v5.0 grading system, the following guidelines will be used to describe severity.

- **Mild** – Events require minimal or no treatment and do not interfere with the subject's daily activities.
- **Moderate** – Events result in a low level of inconvenience or concern with the therapeutic measures. Moderate events may cause some interference with functioning.
- **Severe** – Events interrupt a participant's usual daily activity and may require systemic drug therapy or other treatment. Severe events may be potentially life-threatening or incapacitating.

NOTE: A distinction should be drawn between serious and severe AEs. Severity is an estimate or measure of the intensity of an AE, while the criteria for serious AEs are indications of adverse subject outcomes for regulatory reporting purposes. A severe AE need not necessarily be considered serious and a serious AE need not be considered severe.

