7.2 Definitions for Safety Parameters

Event	Definition
Adverse Event (AE)	The AE observation period starts at the time of signing informed consent and includes baseline or washout periods, even if no study treatment has been administered. AE is any untoward medical occurrence in a subject to whom the IP has been administered, regardless of whether the event is considered related to that product. An AE is also an undesirable medical condition due to a study-related procedure.
Adverse Reaction (AR)	AR is an untoward and unintended response in a subject to an IP. A causal relationship between a trial medication and an AE is at least a reasonable possibility, i.e. the relationship cannot be ruled out.
Serious Adverse	An AE or suspected AR that is considered "serious" if, in the view of either the investigator or Sponsor, it results in any of the following outcomes:

Event	Definition
Event (SAE) or Serious Adverse Reaction (SAR)	
 Death (Note: death is an outcome not an event) A life-threatening AE (an event in which the subject was at risk of death at the time of the event; it does not refer to an event which hypothetically might have caused death if it were more severe) Inpatient hospitalization or prolongation of existing hospitalization A persistent or significant incapacity or substantial disruption of the ability to conduct normal life functions A congenital anomaly/birth defect. Important medical events that may not result in death, be life-threatening, or require hospitalization may be considered serious when, based upon appropriate medical judgment, they may jeopardize the participant and may require medical or surgical intervention to prevent one of the outcomes listed in this definition. Examples of such medical events include allergic bronchospasm requiring intensive treatment in an emergency room or at home, blood dyscrasias or convulsions that do not result in inpatient hospitalization, or the development of drug dependency or drug abuse.

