7.2.1 Events not Qualifying as AEs/SAEs

The following are not considered to be AEs or SAEs:

- Medical or surgical procedures (e.g., endoscopy, appendectomy). The condition that leads to the procedure is considered the AE.

- Elective procedures, planned hospitalizations, and procedures for treatment of conditions noted in the patient's medical history (present prior to signing the ICF) that have not worsened are not considered AEs.
- Situations where an untoward medical occurrence did not occur (i.e., admission to hospital for social circumstances).
- Anticipated day-to-day fluctuations of pre-existing medical conditions that were present at start of study. These conditions are considered part of the patient's medical history and must be adequately documented on the appropriate page of the CRF.
- Clear progression of disease under study should not be reported as an AE or SAE (unless the investigator considers the progression of underlying neoplasia to be atypical in its nature, presentation or severity from the normal course of the disease in a particular patient). Findings that are clearly consistent with the expected progression of the underlying cancer should not be reported as an adverse event, and hospitalizations due to the progression of cancer do not necessarily qualify for an SAE.
- In the case where the medical condition is known when the participant enters the trial, only worsening (increased frequency or intensity of the episodes or attacks) will be documented as an AE. If the disease is detected during the trial, and if repeated episodes enable diagnosis of a chronic disease, the episodes will be grouped together in the CRF, and the diagnosis will be clearly described.
- Laboratory abnormalities: An isolated, out-of-range laboratory result in the absence of any associated, clinical finding may or may not be considered an AE; the Investigator's evaluation should be based on a consideration of the overall clinical context.

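### Mandatory admission for every infusion reaction makes mild IRR/CRS events serious, and the SAP's serious-event tables cannot separate them

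*Protocol*

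**What the plan says.** **Admission.** Protocol Section 3.5.1 states: "In the event of any Grade IRR (including CRS), subjects will be admitted for closer observation until resolution of symptoms". Section 5.6 repeats the rule. In the Section 3.5.1 tables, the Grade 1 and Grade 2 rows for infusion reactions and for CRS each carry the instruction "Admit to hospital for close observation until resolution of symptoms". Section 3.5.1 also says of its guidance: "These guidelines are not meant to be prescriptive". Section 5.6 has no such qualifier.

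**Seriousness.** Section 7.2 lists "Inpatient hospitalization or prolongation of existing hospitalization" among the outcomes that make an event serious. Section 7.5 requires every SAE to reach the sponsor within 24 hours of site awareness, whatever its relationship to treatment. The exceptions in Section 7.2.1 include "Elective procedures, planned hospitalizations, and procedures for treatment of conditions noted" in the medical history that have not worsened, social admissions, and clear disease progression.

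**Grade.** The general scale in Section 7.1 includes "hospitalization or prolongation of hospitalization indicated" under Grade 3. For these reactions, Section 3.5.1 tells sites to "utilize terms based on best medical judgement of the AE/SAE and the definition found in NCI-CTCAE v5.0 for IRR", and likewise for allergic reaction, anaphylaxis and CRS.

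**Analysis.** SAE incidence is among the primary safety outcomes in Protocol Section 2 (Table 4) and SAP Section 2. SAP Section 11.2 plans subject incidence of serious and drug-related serious treatment-emergent events by preferred term (Tables 14.3.1.7 and 14.3.1.9).

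**The concern.** Admission usually carries information: a clinician judged the patient ill enough to need a bed. Here the protocol removes that judgement for one class of event, and then uses admission to decide whether the event is serious. A Grade 1 reaction that is admitted only because the rule says so enters the SAE count alongside a reaction that needed hospital care.

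This affects the toxicity of most interest. Section 1.2.4 names IRRs as the primary concern in the animal studies, and Section 3.5.1 bars primary prophylaxis so that a safety signal is not obscured. At stake is whether serious IRR/CRS counts, by dose level and by expansion cohort, can be read as a measure of clinical consequence. If the reason for seriousness is not recorded when the event occurs, it may not be recoverable later.

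**Working it through.** The plan gives no figure on seriousness. The nearest one is the Section 9.2.2 boundary for Grade 3 or higher IRRs, said to be crossed with probability at most 0.05 at a 30% rate. An exact binomial recursion over 1 to 15 subjects, stopping at the printed limits, gives 0.0447, so that statement stands. The boundary counts events by grade, not by seriousness, so the SAE question does not touch it.

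The rest is a comparison of provisions.

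1. **Is a mild reaction admitted?** Yes. Sections 3.5.1 and 5.6 cover any grade, and the Grade 1 and 2 table rows say so individually.
2. **Is that admission a seriousness criterion?** On its wording, yes. Section 7.2 does not require that the admission be clinically driven.
3. **Does an exception apply?** Not clearly. Planned hospitalizations appear in an item that also covers elective procedures and unworsened conditions from the medical history; a new reaction to the study drug is a different case. The social and disease-progression items do not fit either.
4. **Result.** Under the literal text, 100% of admitted IRR/CRS events are SAEs, at every grade.
5. **Can the planned output separate them?** The serious-event tables are by preferred term, with no split by grade or seriousness criterion. Severity is reported elsewhere: events by maximum grade (Tables 14.3.1.3 to 14.3.1.5), Grade 3 or 4 events (Table 14.3.1.10) and a listing of infusion-reaction signs and symptoms (Listing 16.2.7.13). None is described as showing which events were serious only through the required admission.

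**Size.** Let r be the share of subjects whose only IRR/CRS events are Grade 1 or 2, and s the share of those subjects who have another SAE anyway.

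- Increase in SAE incidence = r × (1 − s), which is at most r.
- The documents give neither r nor s. Assuming r between 10% and 40%, the increase is at most 10 to 40 percentage points.
- In a 15-subject expansion cohort that is at most 0.10 × 15 = 1.5 to 0.40 × 15 = 6 additional subjects with an SAE, on average.

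**The case against.** **The rule is deliberate and errs on the safe side.** Appendix 16.9 shows that any-grade admission was added in Amendment 01, for a first-in-human product with deaths in the animal studies. Prompt reporting of mild reactions can be defended on that ground. This stands, and it is why removing these events from SAE reporting is not proposed.

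**Extra non-fatal SAEs drive no formal decision.** Dose escalation uses dose-limiting toxicities, the expansion boundaries use IRR grade and discontinuations, and the halting rule in Section 7.8 needs a fatal related SAE. This stands, and it limits the severity of the point.

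**Seriousness is not severity, and severity is tabulated separately.** True, and Section 7.1 says so. But SAE incidence is a named primary outcome, and its content should be interpretable.

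**The guidance is not prescriptive, and planned hospitalizations are excepted.** The first softens Section 3.5.1 but not Section 5.6. The second is arguable, but does not clearly reach a new reaction.

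**A stronger reading is tempting.** A reader might infer that mandatory admission meets the Grade 3 descriptor, so that mild reactions become dose-limiting toxicities, lower the MTD and trip the IRR boundary. The documents do not support this. Their tables keep admitted reactions at Grade 1 and 2, Section 3.2.5 treats a Grade 2 IRR as a live category, Section 3.5.1 points to medical judgement and the term-specific CTCAE definition, and Section 7.1 says a serious event need not be severe. Upgrading would require a site to apply the general scale against all of these. Probabilities built on an assumed rate of such misgrading would measure the assumption, not the plan.

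**Conclusion.** The seriousness point holds on the text. Admitted Grade 1 and 2 IRR/CRS events meet an SAE criterion because of a protocol rule, no listed exception clearly removes them, and the planned tables cannot isolate them. A primary safety outcome is therefore partly a measure of the admission rule.

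The size depends on the unknown frequency of mild reactions: up to 10 to 40 percentage points under the assumed range, and nothing if no such reactions occur. It also assumes that sites treat the required admission as inpatient hospitalization; Section 7.2 sets no minimum stay.

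The Grade 3 wording in Section 7.1 is an ambiguity to close, not a stated consequence. No effect on dose-limiting toxicities, the MTD or the expansion boundary is established. Severity is minor to moderate: interpretation of the SAE results is weakened, but no dose decision is shown to go wrong.

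**What to change.** Leave the admission rule and SAE reporting as they are. This point takes no view on when a subject should be admitted.

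1. **Protocol Sections 3.5.1, 5.6 and 7.1.** Reconcile these with one sentence saying that IRR and CRS are graded on the CTCAE v5.0 term definition, and that the required admission does not itself determine the grade.
2. **eCRF.** Add a flag for IRR/CRS events whose only seriousness criterion is the admission required by Sections 3.5.1 and 5.6, completed by the investigator when the event is reported.
3. **SAP Section 11.2.** Present serious and drug-related serious treatment-emergent events (Tables 14.3.1.7 and 14.3.1.9) with and without flagged events.

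The cost is a sentence of protocol text, one eCRF field and one extra set of tables. IRR/CRS events already recorded would need a query to fill the field. The flag relies on the investigator's judgement that nothing else made the event serious, so the version with all events should remain the main table.

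### Protocol Section 3.5.1 leaves two points unreconciled: the Grade 2 CRS steroid entry against the Grade 3 and 4 entries, and the Grade 2 restart rule for IRR against that for CRS

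*Protocol*

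**What the plan says.** All the text at issue is current wording in Protocol Section 3.5.1.

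**Steroid entries in the cytokine-release table**
- Grade 2: alongside antipyretics and H1/H2 antagonists, joined by and/or, the row lists "methylprednisolone 1-2 mg/kg or equivalent dose of corticosteroid every 6 hours". It adds "Subjects with worsening symptoms should be treated as for Grade 3", and directs older subjects and those with extensive comorbidities to Grade 3 management too.
- Grades 3 and 4: both rows put tocilizumab first. Under second-line therapies each gives "Methylprednisolone 2 mg/kg/day IV tapered over several days".

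**Restart entries for a Grade 2 event**
- IRR table: the infusion is either slowed by half or interrupted. "If the infusion is interrupted, then restart the infusion at no more than 50% of the rate at which the reaction symptoms occurred". Then: "If symptoms recur, then no further investigational product (IP) will be administered at this visit".
- CRS table: "Interrupt IP and do not-restart until symptoms are returned to grade ≤1 for at least 3 days". Dosing then resumes at the next scheduled time point.

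**How the two tables relate**
- The introduction says: "General guidance is provided below for IRRs secondary to both allergic and non-allergic HSRs e.g., CRS".
- On allergic and non-allergic reactions it says: "There are no specific clinical features (including symptoms and timing of reaction) that can absolutely distinguish between these two entities".
- Final etiology is to be determined once the event has resolved, using symptoms, treatment response and laboratory results.

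**The concern.** Infusion reactions were the primary toxicity of concern in the monkey studies (Section 1.2.4), and Section 1.4.1 expects CRS from the mechanism of action. Section 3.5.1 is therefore the part of the protocol that sites are most likely to need at short notice.

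Two features of it are hard to follow as printed. First, a subject who moves from the Grade 2 CRS row to the Grade 3 row meets a lower stated daily steroid figure, written in a different unit, with no explanation. Second, a Grade 2 event that could be CRS or another kind of IRR fits two rows with incompatible restart instructions. Two sites could act differently on the same presentation and each be following the table. What is at stake is consistent handling of the main anticipated risk.

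**Working it through.** **Steroid entries**

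Inputs, from the cytokine-release table:
- Grade 2: 1 to 2 mg/kg per administration, at 6-hour intervals.
- Grades 3 and 4: 2 mg/kg/day.

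The Grade 2 row prints no daily total, so the plan has no figure of its own to reproduce. The daily amount below assumes that the 6-hourly schedule runs for a full 24 hours.

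1. Administrations per day: 24 / 6 = 4.
2. Grade 2 daily amount: 4 × 1 = 4 to 4 × 2 = 8 mg/kg/day.
3. Ratio to Grades 3 and 4: 4 / 2 = 2 to 8 / 2 = 4.
4. Fall on moving from the Grade 2 to the Grade 3 row: 1 − 2/4 = 50% to 1 − 2/8 = 75%.

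Sensitivity to how many Grade 2 administrations are given in the day:

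| Administrations in 24 h | Grade 2 amount (mg/kg) | Ratio to 2 mg/kg/day |
|---|---|---|
| 1 | 1 to 2 | 0.5 to 1 |
| 2 | 2 to 4 | 1 to 2 |
| 3 | 3 to 6 | 1.5 to 3 |
| 4 (as printed) | 4 to 8 | 2 to 4 |

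The reversal disappears if a single administration was meant. The same holds if 1 to 2 mg/kg was meant as a daily total. The row states neither.

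**Restart entries, side by side**

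| | Grade 2 IRR row | Grade 2 CRS row |
|---|---|---|
| Infusion in progress | Interrupt, or run at half rate | Interrupt |
| Restart | Same visit, at no more than half the earlier rate | Not until Grade 1 or lower for at least 3 days |
| Hospital admission | Yes, until symptoms resolve | Yes, until symptoms resolve |

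That the IRR restart falls within the same visit follows from the next instruction in that row, which ends dosing for the visit only if symptoms come back.

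The introduction places CRS inside the IRR guidance, so a Grade 2 event of unsettled cause is covered by both rows. The first choice, whether to interrupt or only slow the infusion, has to be made while symptoms are present, before the etiology review. Nothing in the section says which row governs in the meantime.

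**The case against.** The case on the other side has real force.

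- **The steroid rows describe different treatment situations.** At Grade 2 the steroid is one optional item. At Grades 3 and 4 it is second-line, behind tocilizumab and intensive monitoring. A reader might infer that care is reduced as severity rises. The documents do not support that: the higher-grade rows add agents and monitoring. What stands is narrower: the stated steroid figure falls, and the unit changes, without explanation.
- **4 to 8 mg/kg/day is derived, not printed.** This is correct. The row gives no duration, so the figure depends on the 24-hour assumption.
- **The two reactions are not declared indistinguishable.** A reader might infer that IRR and CRS cannot be told apart. The text says only that no clinical feature separates allergic from non-allergic reactions absolutely. It lists symptoms that point towards allergy, and asks for medical judgement with separate CTCAE terms. What stands is that doubt is foreseen and no interim rule is given.
- **Restart and etiology review may coincide.** The IRR row interrupts or slows the infusion until the event resolves, which is also when etiology is reviewed. This weakens the timing argument where the infusion is interrupted. It does not cover the option to keep infusing at half rate, and laboratory results may still be outstanding.
- **The guidance is non-prescriptive** and gives way to institutional guidelines where appropriate. Both Grade 2 rows require admission, and Section 5.5 requires a physician on site or immediately available. This lowers the practical risk but does not reconcile the rows, which use directive wording.

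**Conclusion.** The point holds as two specific inconsistencies in Section 3.5.1 that should be clarified.

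1. The Grade 2 CRS steroid entry, continued for 24 hours as printed, is 2 to 4 times the Grade 3 and 4 entry. The escalation link therefore lowers the stated daily figure by 50 to 75%. This rests on reading the entry as four administrations in the day.
2. The Grade 2 restart rules differ between the same visit and at least 3 days at Grade 1 or lower, and no text assigns a Grade 2 event of unsettled cause to either row.

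A reader might go further and infer distorted DLT evaluability or toxicity discontinuations. The documents do not show that:
- Cycle 1 doses are 7 days apart, so a 3-day hold can fit between doses if symptoms settle within about 4 days (7 − 3).
- Schedule 1 evaluability needs only two doses (Section 9.3).
- Grade 2 IRR and CRS are not among the Grade 2 DLTs listed in Section 3.2.6.
- The expansion boundary for IRRs counts Grade 3 and above (Section 9.2.2).
- Neither Grade 2 row calls for permanent discontinuation.

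No effect on these or other endpoints is claimed, and no sample size, power or error rate is involved.

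**What to change.** The sponsor's clinical team should:

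- reconcile the Grade 2 CRS steroid entry with the Grade 3 and Grade 4 entries, writing unit and interval the same way in all three rows and, if the difference is intended, saying why;
- reconcile the Grade 2 IRR and Grade 2 CRS restart instructions by stating which row applies while the cause of the event is unsettled.

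The content of both is a clinical decision, and nothing here indicates which dose or rule is right. The cost is table wording in the next amendment, or a clarification letter to sites. No analysis changes.
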